# 7.2 Hypotheses

It is hypothesised that:

- 1. The H1 will demonstrate non-inferiority in terms of survivorship compared to the BHR
- 2. The H1 will be demonstrated to be superior in terms of toxicology compared to the BHR

Please refer to Section 10 for more details regarding the null hypotheses and sample size calculations.

## 7.3 Outcome Measures

#### 7.3.1 Preliminary Safety Study Outcome Measures (Cohort 1A)

- Complication rate (adverse events and revisions)
- Toxicology (blood metal ion measurements)
- CT assessment (Implant migration, osseointegration)

#### 7.3.2 Second Safety Study Outcome Measures (Cohort 1B)

- Complication rate (adverse events and revisions)
- Toxicology (blood metal ion measurements)
- CT assessment (Implant migration, osseointegration)

## 7.3.3 Safety and Efficacy Study Outcome Measures (Cohort 1A, 1B, 2)

- Implant survivorship
- Patient Reported Outcome Measures (PROMs)
- Objective clinical and functional outcomes (Harris Hip Score, Gait Analysis)
- Radiological assessment (implant orientation, osseointegration)

# 8 Investigation Design and Endpoints

- 8.1 General
- 8.1.1 Type of investigation

This is a multi-centre, prospective, non-randomized, observational study to evaluate the clinical outcome of the H1 hip resurfacing implant.

In order to evaluate the safety of the new device, the study will be subdivided in a shortterm safety study and a long-term safety and efficacy study. The safety study (Cohort 1A – 20 patients) will record complication rate, toxicology and radiological assessment. Cohort 2 will consist of the remaining patients due to undergo a primary hip arthroplasty. Owing to the observation of femoral crush fractures in the first cases undertaken, a second safety cohort will be undertaken - Cohort 1B. Cohort 1B will consist of a further 46 patients.

The data from the study will also be used to compile a report for submission to the manufacturer's notified body in order to obtain a CE marking for the H1 HRA. If the H1 receives a CE mark at this stage, an amendment will be placed to the main REC and the competent authority in order to continue with the study as a post-market surveillance of a CE Marked device as per assessments listed in the schedule of procedures. If the CE marking is not obtained at that point, the study will continue as per protocol.

See the flow diagrams in Figure 1 to Figure 3 for a graphical explanation of the investigation plan.

#### 8.1.2 Investigation bias

#### **Improper Influence**

The sponsor and all investigators shall avoid improper influence on, or inducement of, the subject, monitor, any investigator(s) or other parties participating in, or contributing to, the clinical investigation.

#### Patient recruitment and screening

To eliminate the potential for selection bias, investigators will consecutively screen all their patients who could be eligible for an H1 HRA. Patients meeting the eligibility criteria will be approached for informed consent and subsequent enrolment in the investigation. Screening efforts must be documented on a screening and enrolment log, on which reasons for exclusion from or denial to participate should be noted.

Participants suitable for hip resurfacing arthroplasty will be identified from the clinic list and theatre waiting list. Those patients meeting the inclusion/exclusion criteria will be given the option to take part. All participants will be given both verbal and written explanation of the study by an appropriately experienced and informed clinician. No pressure will be placed on participants, nor time pressure imposed to make a quick decision. A minimum of twenty-four-hours will be required before decision to participate will be accepted. The patient will be given the opportunity to ask questions and highlight any concerns they may have. Patients will be told they are free withdraw at any time. If participants wish to take part, they will be asked to sign the study informed consent form.

Women of child-bearing age will be asked about their method of anticonception, which will be noted in the Conmed section prior to inclusion in the study and prior to every imaging (X-ray or CT scan) as usual. If a female participant does become pregnant during the study, imaging will be postponed until after the childbirth but questionnaires will be performed as planned.

#### Independent assessor

At each participating site, an independent assessor will be assigned for the study-related clinical and radiological follow-up of the patients included into the study to avoid bias. The independent assessor should not be the surgeon who performed the total hip arthroplasty but another surgeon, physician, research nurse or research assistant properly trained in the clinical follow-up of the patients and the correct completion of the Case Report Forms. The official independent assessor will be assigned on the delegation log at each study site.

Safety analysis of Cohort 1A and Cohort 1B (first 14 patients only) will be reviewed by independent assessors from the Karolinska Institute in Stockholm, Sweden, who are experts in assessing safety and performance of hip replacement including implant migration. At a later stage those independent assessors will also evaluate the anonymised clinical and radiographic outcome of Cohort 1A, Cohort 1B and Cohort 2 until the 2 year postoperative time point.

# Advancing musculoskeletal

#### 8.1.3 Endpoints

#### **Primary Endpoint**

Revision for any reason

#### **Secondary Endpoints**

- Complication rate (adverse events and revisions)
- Toxicology (blood metal ion measurements)
- CT assessment (Implant migration)
- Patient Reported Outcome Measures (PROMs)
- Objective clinical and functional outcomes (Harris Hip Score, Gait Analysis)
- Radiological assessment (implant orientation, osseointegration)

The primary endpoint will be revision of the H1 prosthesis for any reason. However, since hip resurfacing components are considered to be easy to revise, the threshold for revision may be lower than for a total hip arthroplasty. Therefore, the secondary endpoints of the H1 ceramic-on-ceramic and comparison with Metal-on-metal hip resurfacing and with conventional Total Hip Arthroplasties is considered to be a very important discriminating factor as well. Secondary endpoints will investigate the short-(6 months, 1 year, 2 years, 3 years), mid- (5, 7 years) and long-term (10 years) safety and efficacy of the H1 hip resurfacing prosthesis for the whole patient cohort.

In the Cohort 1A and 1B, cementless acetabular and femoral component migration, and bone ongrowth will be assessed on low-dose CT scans. Absence of generation of metal wear debris potentially leading to local adverse tissue reactions and systemic toxicity will also be assessed by measuring metal ions (cobalt, chromium) in whole blood. Metal ion blood levels will be compared to historical metal ion measurements from MoM hip resurfacings and publications in the orthopaedic literature.

## 8.2 Data Collection

The assessments and data collection are detailed in Part C, Procedures.

## 8.2.1 All participants (Cohort 1A, Cohort 1B, Cohort 2)

#### **Baseline Data**

Baseline data collection will include imaging, clinical questionnaires, demographical data, medical history and data related to the surgery and the implant used. All patients in the study will undergo hip resurfacing with the H1 hip implant. Operative data will be collected along with discharge information.

#### Patient Reported Outcome Measures and objective clinical and functional outcomes

Data that will be collected as part of the clinical follow-up will include x-rays and subjective hip and general health clinical evaluation including PROMs (Harris Hip Score (HHS) and the Oxford Hip Score (OHS) [39]). The patients' opinion about their state of health, according to a visual analogue scale and 5 dimensions - mobility, self-care, usual activities, pain/discomfort and anxiety/depression, (each dimension having 5 levels: no problems, slight problems, moderate problems, severe problems and extremely) - will be assessed with the EQ-5D questionnaire [40]. Patient satisfaction, expectations and a self-assessment of the physical outcome will also be done according to the new Imperial Score evaluating pain, function and fulfilment of preoperative aspirations after hip arthroplasty. The Imperial Score can only be collected online.

#### **Radiological Assessment**

Radiological evaluation at the scheduled follow-up intervals (see flow diagram in Figure 1 to Figure 3 and Schedule of procedures in Table 2 to Table 8) will include standard anteroposterior (AP) pelvis and lateral hip radiographs, or 3D CT-series where available.

#### **Complication Rate**

Adverse Events (AE), Serious Adverse Events (SAE), complications and revisions and causal relation of the complication to the implant and/or surgery will be recorded

whenever applicable. The sponsor and manufacturing company (both Embody Orthopaedic Ltd), the Ethics committees, regulatory authorities will be notified of any device related adverse events and of all SAE, device related or not device related as further outlined in Section 16.

In the unlikely event of an early failure and revision, thorough tissue, fluid and implant retrieval analysis will be performed in order to detect the exact cause of failure. Steps will be put in place to monitor patients on the study, please see Section 15.1.

## 8.2.2 Cohort 1A Only

#### **CT** Assessment

Cohort 1A (first 20 patients) will undergo a low dose CT scan preoperatively and postoperatively at 6 months and an ultra-low dose CT scan at the following time points: immediately postoperatively (2days), 6 weeks, 3 months, 1 year and 2 years. This will be used to evaluate the interfaces between implants and bone to assess possible migration of the acetabular and femoral components based on tantalum markers.

#### Toxicology

Metal ion exposure questionnaires will be collected pre-operatively only. Metal ion testing (whole blood Co, Cr, and Ti, concentrations) will be performed in all Cohort 1A patients. Co ion testing is performed as a confirmation of the absence of Co as opposed to the standard metal-on-metal hip resurfacings. Cr ions are expected to remain below the detection limit as outlined above. Ti ions may be present as part of the bone ongrowth process of the non-cemented components, but are not associated with toxic reactions as outlined in section 1. Since previous studies have demonstrated that ceramic-on-ceramic bearings are not associated with adverse metal ion release it is not deemed necessary to subject all patients to metal ion testing provided the results from the Cohort 1A patients confirm the absence of metal ions release at 3, 6, 12 and 24 months postoperatively. With well-functioning metal-on-metal hip resurfacing a characteristic 9-12 months run-in phase of metal ion release.

#### 8.2.3 Cohort 1B Only

#### **CT** Assessment

Cohort 1B (46 patients) will undergo a low dose CT scan preoperatively and an ultra-low dose CT scan at the following time points: immediately postoperatively (2days), 6 weeks, 3 months, 6 months, 9 months, 1 year and 2 years. This will be used to evaluate the interfaces between implants and bone to assess possible migration of the acetabular and femoral components based on tantalum markers.

#### Toxicology

Metal ion exposure questionnaires will be collected pre-operatively only. Metal ion testing (whole blood Co, Cr, and Ti, concentrations) will be performed in the first 14Cohort 1B patients. Co ion testing is performed as a confirmation of the absence of Co as opposed to the standard metal-on-metal hip resurfacings. Cr ions are expected to remain below the detection limit as outlined above. Ti ions may be present as part of the bone ongrowth process of the non-cemented components, but are not associated with toxic reactions as outlined in section 1. Since previous studies have demonstrated that ceramic-on-ceramic bearings are not associated with adverse metal ion release it is not deemed necessary to subject all patients to metal ion testing provided the results from the Cohort 1B patients confirm the absence of metal ions release at 3, 6, 12 and 24 months postoperatively. With well-functioning metal-on-metal hip resurfacing a characteristic 9-12 months run-in phase of metal ion release is followed by a steady-state phase of much lower and decreasing metal ion release.

# 8.3 Data Analysis

#### 8.3.1 Cohort 1A Only

Short-term safety evaluation will be performed in the first 20 patients recruited into the study, which will include data analysis at 2 days, 6 weeks 3 months and 6 months. This short-term analysis will include: complication rate and radiological assessment at 2 days; complication rate, functional assessment and radiological assessment at the 6-week interval; and complication rate, CT assessment, functional assessment and toxicology at the 3 month and 6 month intervals. Metal ion blood levels will be compared to historical metal ion measurements from MoM hip resurfacings and publications in the orthopaedic literature. The safety evaluations shall be independently reviewed by the Karolinska Institute in Stockholm, Sweden.

If the safety analysis at 2 days shows no impact on patient safety (no unanticipated intraoperative or postoperative complications, no issues regarding implant seating) recruitment will commence for Cohort 2. At 3 months, a second evaluation will include a toxicological report (metal ion measurements) which is expected to confirm the safety since the material does not contain toxic elements (no Cobalt, very low amount of non-toxic Chromium 3+) and CT-scans evaluating migration of the non-cemented components.

If the safety analyses of Cohort 1A suggest further investigation, the study will be put on hold until the results of the investigation have been obtained. If those suggest the implant is not safe, the study will be terminated. If the investigation supports the safety of the implant, the study will proceed.

CT analyses will evaluate migration at 6 weeks, 3 months, 6 months, 1 year and 2 years whilst yearly follow-up will be performed until 10 years, and radiographs at 3, 5, and 10 years.

# 8.3.2 Cohort 1B Only

Safety evaluations will be performed on a second set of 46 patients at 6 and 12 months. These analyses will include complication rate, toxicology, CT assessment and functional assessment. The safety evaluations shall be independently reviewed by the Karolinska Institute in Stockholm, Sweden.

If the safety analysis at 6 months shows no impact on patient safety (no unanticipated intraoperative or postoperative complications, no issues regarding femoral crush fractures) recruitment will resume for Cohort 2.

CT analyses will evaluate migration at 6 weeks. 3 months, 6 months, 9 months, 1 year and 2 years.

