## 8.3.4 Analysis reporting time-points

## Table 1 Reporting time-points

Report Title	Time point	Cohort(s)	Independent Review?	Data	
Gateway Safety Analysis 1	2 days	1A	Yes	Complication rate, Radiological Assessment	
Safety Evaluation 6 weeks	6 weeks	1A	Yes	Complication rate, Functional Outcomes, Radiological Assessment	
Safety Evaluation 3 months	3 months	1A	Yes	Complication rate, Functional Outcomes, CT Assessment, Toxicology	
Safety Evaluation 6 months	6 months	1A	Yes	Complication rate, Functional Outcomes, CT Assessment, Toxicology	
Gateway Safety Analysis 2	6 months	1B	Yes	Complication rate, Functional Outcomes, CT Assessment, Toxicology	
Interim Analysis 6 months	6 months	1A,1B,2	Yes	Complication rate, Functional Outcomes, CT Assessment (Cohort 1A and 1B only), Toxicology (Cohort 1A only), PROMS, Survivorship	
Safety Evaluation 1 year	1 year	1B	Yes	Complication rate, Functional Outcomes, CT Assessment, Toxicology	
Interim Analysis 1 year	1 year	1A,2	Yes	Complication rate, Radiological Assessment, Functional Outcomes, CT Assessment (Cohort 1A and 1B only), Toxicology (Cohort 1A only), PROMS, Survivorship	
Interim Analysis 2 years	2 years	1A,1B,2	Yes	Complication rate, Radiological Assessment, Functional Outcomes, CT Assessment (Cohort 1A and 1B only), Toxicology (Cohort 1A only), PROMS, Survivorship	
Interim Analysis 3 years	3 years	1A,1B,2	No	Complication rate, Radiological Assessment, Functional Outcomes, PROMS, Survivorship	
Interim Analysis 4 years	4 years	1A,1B	No	Complication rate, PROMS, Survivorship	
Interim Analysis 5 years	5 years	1A,1B,2	No	Complication rate, Radiological Assessment, Functional Outcomes, PROMS, Survivorship	
Interim Analysis 6 years	6 years	1A,1B	No	Complication rate, PROMS, Survivorship	
Interim Analysis 7 years	7 years	1A,1B,2	No	Complication rate, Functional Outcomes, PROMS, Survivorship	
Interim Analysis 8 years	8 years	1A,1B	No	Complication rate, PROMS, Survivorship	
Interim Analysis 9 years	9 years	1A,1B	No	Complication rate, PROMS, Survivorship	
Final Analysis 10 years	10 years	1A,1B,2	No	Complication rate, Radiological Assessment, Functional Outcomes, PROMS, Survivorship	

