## 9.9 Enrolment Period

Cohort 1A will be recruited within 6 months of investigation start date.

Cohort 1B will be recruited within 6 months of investigation resumption date.

Cohort 2 (pre-upgrade) will be recruited within 1 year of local site approval.

Cohort 2 (post-upgrade) will be recruited within 1 year of local site approval or within 1 year of the clinical trial restart after design upgrade, whichever is longer.

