# 18 Suspension or Premature Termination of the Clinical Investigation

Analysis reports are scheduled as outlined in Table 1. If the analysis report is said to have a significant impact on patient safety, the study will be suspended or terminated accordingly. If the study is temporarily suspended, a full report will be sent to both the ethics committee and competent authority with corrective plans and actions to allow for continuation of the study. While the study is suspended, no new patients will be recruited, however patients registered thus far will continue to follow the schedule of visits as detailed in the table of schedule of procedures. If the study is terminated, patients will be contacted and the findings discussed at the earliest time possible. Patients will be invited back to clinic to discuss the issue with them.

Patients lost to follow up or who choose to withdraw will be followed up by healthcare professionals accordingly. The investigator will decide on the nature and frequency of the follow-up as long as the patient is happy with it. For example, the investigator may deem it acceptable to follow up via telephone call, where they may be asked about adverse events if the patient is happy for the follow up to continue this way. If the study is terminated early, these patients will be notified and asked to attend a clinic appointment for further discussion.

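### Cohort 1B, opened because of femoral crush fractures, gets its first scheduled safety report at 6 months, by which time all 46 patients can already be implanted

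*Protocol*

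**What the plan says.** Section 8.1.1 gives the reason for the cohort: "Owing to the observation of femoral crush fractures in the first cases undertaken, a second safety cohort will be undertaken". It also gives the size: "Cohort 1B will consist of a further 46 patients". Section 3.1 adds that the instrumented technique and the implant rim were changed before the restart.

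- **Evaluations.** Section 8.3.2 says "Safety evaluations will be performed on a second set of 46 patients at 6 and 12 months". In Table 1 the 2-day, 6-week and "Safety Evaluation 3 months" rows list Cohort 1A alone. The earliest rows that include 1B are "Gateway Safety Analysis 2" and the 6-month interim analysis.
- **Scans.** Section 8.2.3 schedules postoperative CT in 1B immediately after surgery and then at "6 weeks, 3 months, 6 months, 9 months, 1 year and 2 years". Table 11 gives implant migration as the reason for the 6-week and 3-month scans, and Section 8.3.2 says that migration will be analysed at those times.
- **Recruitment.** Section 9.9: "Cohort 1B will be recruited within 6 months of investigation resumption date". It describes no stagger or pause.
- **Consequences.** Section 18, referring to the Table 1 reports, says "If the analysis report is said to have a significant impact on patient safety, the study will be suspended or terminated accordingly". The explicit provision to put the study on hold, investigate and then terminate or proceed is in Section 8.3.1 and names the safety analyses of Cohort 1A. Section 8.3.2 says only what follows if the 6-month result is favourable: Cohort 2 reopens.

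**The concern.** A cohort opened to test whether a known problem has been solved would be expected to have at least the early scheduled reviews given to the 20 patients treated before the problem was known. It has fewer. The 6-month gate decides whether Cohort 2 reopens. It is timed so that it need not influence any implantation within Cohort 1B. If the changes to technique and rim have not worked, the whole second cohort can be exposed before anyone is scheduled to report on it. Migration data that might bear on this are being collected and analysed in the meantime, with no report, independent review or decision attached.

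**Working it through.** The protocol gives no calculation for the 46 patients or for the timing of the gate, so there is no stated figure to reproduce. The check compares the recruitment window with the earliest 1B report.

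**Inputs.** 46 patients (Section 8.1.1); recruitment within 6 months (Section 9.9); first 1B report at 6 months after surgery (Section 8.3.2, Table 1); CT at 6 weeks and 3 months (Section 8.2.3, Tables 3 and 11); independent review of the first 14 patients of 1B (Section 8.1.2). Assumptions: even accrual, and surgery at enrolment.

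**Formula.** Rate = 46/6 = 7.67 per month. Implanted at month t = min(46, 7.67 × t). The 14th patient is implanted at 14/7.67 = month 1.83. Six weeks = 6/4.345 = 1.38 months.

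| First 14 patients reach | Month | Implanted | Not yet implanted |
|---|---|---|---|
| 6-week CT | 1.83 + 1.38 = 3.21 | 24.6 | about 21 |
| 3-month CT | 1.83 + 3 = 4.83 | 37.0 | about 9 |
| 6-month CT | 1.83 + 6 = 7.83 | 46 | 0 |

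The last row does not depend on which patients form the gate. The first patient reaches 6 months at month 6, when accrual is complete; the last reaches it at month 12.

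**Allowing for delay.** Table 3 gives a visit window of ±2 weeks. Two weeks are 2/4.345 = 0.46 months, or 0.46 × 7.67 = 3.5 further implants, which takes the 9 at 3 months down to 5 or 6. Add 3 weeks for migration analysis and review (an assumption), making 5 weeks in all: 5/4.345 = 1.15 months, or 8.8 further implants. Then:

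- at 6 weeks: 21.4 − 8.8 = 12.6 not yet implanted
- at 3 months: 9.0 − 8.8 = 0.2, close to none

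**Sensitivity of the 6-month result.**

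- Accrual over 3 or 4 months: all 46 implanted when the first patient reaches 6 months.
- Accrual over 9 months (an overrun): 46/9 × 6 = 30.7, about 31 implanted.
- First patient operated on at once and the others after a longer wait: (6 − 1) × 7.67 = 38 with a 1-month lag, and (6 − 4) × 7.67 = 15 with a 4-month lag. Four months is the upper limit of the preoperative window in Table 3. A lag common to all patients changes nothing.

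**The case against.** The strongest defence is that the 1B gate is stricter than the 1A gate where it matters most. In Cohort 1A, a 2-day analysis opened Cohort 2, so the 6-week and 3-month reports protected a cohort that could already be recruiting. Cohort 2 now stays shut until the 6-month gate, which caps exposure at 46 patients. This stands, but it protects later patients rather than those in 1B.

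Secondly, Section 3.1 says the movement appeared in 6-month data and mentions no signal from the earlier 1A evaluations. Early looks may therefore be less sensitive. That also stands, although the protocol does not give it as a reason for omitting them. A reader might want to attach a probability that an early look would detect movement. The documents give neither a fracture rate nor any basis for movement being visible that early, so no such figure is supported.

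Three further inferences go too far:

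- *Nothing can stop 1B before month 6.* Section 16.3 requires immediate reporting of serious and device-related events, Section 12.5 provides central monitoring of safety signals, and reports on other cohorts may fall due, though they would concern patients treated before the upgrade. Section 18 does not say that only a Table 1 report can suspend the study.
- *The problem is visible only on CT.* Section 3.1 credits safety data, not CT, and reports crush fractures in Cohort 2, which has no postoperative CT in Table 4.
- *The early scans are unused.* Section 8.3.2 says they are analysed. What is missing is a scheduled report.

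The Cohort 1B flow diagram is not available here, so an interim check shown only there cannot be excluded.

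**Conclusion.** The point holds in a limited form. On the protocol's text, all 46 Cohort 1B patients can be implanted before the first scheduled report on that cohort, and early migration data feed no scheduled report or independent review. This follows whenever accrual takes 6 months or less and the wait for surgery is similar across patients. It weakens if recruitment overruns or later patients wait longer, and the plan guarantees neither.

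The practical gain from earlier reports lies mainly at 6 weeks: about 21 patients not yet implanted without delay, or 12 to 13 with about 5 weeks of delay. At 3 months it is about 9 falling to almost none. These numbers describe patients who could still be affected by a decision, not fractures avoided. The plan contains no arithmetical error here. This is a worthwhile, inexpensive improvement to safety reporting, together with two places where the text needs reconciling.

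**What to change.** 1. Add Cohort 1B rows to Table 1 at 6 weeks and 3 months, naming complication rate and CT assessment, and align Section 8.3.2. Adding 1B to the existing 6-week row would not do this: that row lists radiological rather than CT assessment, and Table 3 has no 6-week radiograph for 1B.
2. Report on patients as they reach each visit, without waiting for the whole cohort, to the independent assessors already engaged. Keep Gateway Safety Analysis 2 at 6 months.
3. Reconcile Sections 8.3.1, 8.3.2 and 18 so that the text says whether the hold provision covers Cohort 1B. Which rule applies is for the sponsor and investigators to decide.
4. Reconcile Section 8.1.2 (independent review of the first 14) with Section 8.3.2 (evaluation of 46) on which patients form the gate.

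The cost is two short reports and some reviewer time. No scans, visits or patients are added. The limitation is that an uneventful early report would be weak reassurance, since the first signal was recognised only at 6 months.
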